1. ABBREVIATIONS

AL: Local Anesthesia

ALR: Regional Anesthesia

ANSM: French National Agency for Medicines and Health Products Safety

ARC: Clinical Research Associate

CMC: Medical-Surgical Center

CNIL: National Commission for Information Technology and Civil Liberties

CPP: Committee for the Protection of Persons

ECG: Electrocardiograph

ENA: Analog-to-Digital Scale

ENR: Digital Recognition Scale

HV: Hallux Valgus

MR: Reference Methodology

NIBP: Non-Invasive Blood Pressure

RICAP: Research and Innovation at the Ambroise Paré Medical Center

SpO2: Pulse Oximetry

PIVC: Peripheral Intravenous Catheter

2. SCIENTIFIC RATIONALE AND GENERAL DESCRIPTION OF THE RESEARCH

2.1. Study Context

Surgery for forefoot conditions (such as hallux valgus, ingrown toenails, foot wounds, metatarsal fractures, Morton's neuroma, etc.) is a painful procedure typically performed on an outpatient basis. Effective pain management is crucial, and regional anesthesia (RA) is currently the gold standard technique (1–3). Blockade of the sciatic nerve and/or its branches is the most appropriate analgesic technique. The innervation of the foot depends exclusively on this nerve.

The sciatic nerve block has long been performed in the popliteal fossa or on the thigh (4). However, this technique causes motor block of the tibialis anterior and triceps surae muscles. The former causes a steppage gait, while the latter results in an inability to lock the knee. Early resumption of walking therefore requires the use of a knee brace and canes (5). This technique, long used for hospitalized patients, is therefore poorly suited for outpatient forefoot surgery.

Trunk blocks of the distal branches of the sciatic nerve (tibial and fibular) at the ankle have been considered to maintain ankle joint mobility, thereby facilitating early discharge home while ensuring effective pain relief (6,7) (Figures 1 and 2). The tibial nerve block at the ankle allows for anesthesia of the various branches of this nerve: the medial plantar branch (medial plantar nerve), the lateral plantar branch (lateral plantar nerve), and the calcaneal branches. This block is combined with blocks of the deep and superficial peroneal nerves. This technique is an effective alternative for forefoot surgery. Nevertheless, the loss of cutaneous sensation and deep (or proprioceptive) sensation in the heel theoretically carries a risk of falling. Indeed, the loss of proprioception results in the abolition of the medial plantar reflex (flexion of the toes upon percussion of the plantar arch), as well as an absence of muscle contraction of the triceps surae. Early discharge is therefore feasible, either without weight-bearing using crutches, or with cautious weight-bearing and crutches, for patients who have been informed of the risk of falling.

[figure not shown]

Figure 1: Anatomy of the sciatic nerve

[figure not shown]

Figure 2: Branches of the sciatic nerve at the ankle

2.2. Research Hypothesis

Specific anesthesia of the distal foot, sparing the heel, would allow for both effective pain relief and safe resumption of walking with exclusive heel support in a postoperative off-loading shoe (such as a Barouk shoe).

Ultrasound allows for precise localization of the nerves and their distal branches. The specific localization and anesthesia of the branches innervating the forefoot (medial and lateral plantar nerves) could meet this dual objective: effective pain relief and safe resumption of walking.

A specific approach to these two distal branches of the tibial nerve could be considered at the medial border of the foot, along a line connecting the center of the medial malleolus and the medial calcaneal tuberosity (MC axis = flexor retinaculum) (Figure 3). The calcaneal branch of the tibial nerve generally originates in the medial retromalleolar region, above the MC axis.

[figure not shown]

Figure 3: Anatomy of the flexor retinaculum

The objective of this study is to evaluate the feasibility and safety of a specific anesthesia of the distal foot, preserving sensation in the heel, for forefoot surgery.

2.3. Summary of benefits, if any, and foreseeable and known risks for participants in the study

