2.3.1. Expected benefits for the patient

The objective of this study is to provide long-lasting analgesia for forefoot surgery, while promoting early resumption of unassisted walking (without crutches or splints) and rapid discharge from the hospital.

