3. RESEARCH OBJECTIVES

3.1. Primary objective

The primary objective of the study is to evaluate the feasibility and safety of a specific anesthesia technique for the distal foot, preserving sensation in the heel.

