4. EVALUATION CRITERIA

4.1. Primary Endpoint

The primary endpoint is the success of the procedure, defined as the successful selective block of the plantar branches of the tibial nerve, anesthesia of the distal foot while preserving heel sensation, and the absence of paresthesia.

The success of the selective block of the plantar branches of the tibial nerve will be assessed using a sensation score for each branch of the tibial nerve.

A cold test and a touch test will be performed every 10 minutes for 40 minutes following the injection of local anesthetics.

The touch test will be performed using a 2-point sensitivity measurement device (Touch-Test).

The cold test will be performed using a cold roller (Rullo “Oerlikon” nizell.ch).

The tests will be performed on specific areas of the tibial nerve:

- calcaneal branches: calcaneus;
- medial plantar nerve: medial part of the arch of the foot;
- lateral plantar nerve: lateral part of the arch of the foot.

A contralateral assessment will be performed to accurately determine the sensory score.

Score/Contralateral side: 2: normal sensation, 1: decreased sensation, 0: total loss of sensation.

The success of the selective block will be confirmed if the following results are obtained at 40 minutes:

- calcaneal branches = 2
- medial plantar nerve = 0
- lateral plantar nerve = 0

At 40 minutes, a precise mapping of the plantar arch will be performed to determine the exact extent of sensory loss (Figure 4).

The degree of paresthesia during the procedure will be assessed by asking the patient about any sensations of discomfort: tingling, numbness, or other prickling sensations.

[figure not shown]

Figure 4: Example of a plantar arch mapping

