12.5. Identification of all data to be collected in the observation log

Demographic data:

- Age
- Gender
- Height
- Weight

Preoperative data:

- Date of surgery
- Type of surgery
- Intraoperative events: Use of standard anesthesia technique
- Volume of local anesthetic per nerve
- Time of regional anesthesia, time of surgery, time of surgery completion
- Sensory scores (from the cold test and touch test) recorded every 10 minutes during the 40 minutes following local anesthetic injection,
- Mapping of the plantar arch based on sensory scores,

- ENR-Plantar nerves
- ENA-VVP
- ENA-ALR
- ENA-Satisfaction
- Intraoperative complications

Postoperative data:

- Possible complications (see Appendix 1: questionnaire)

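### Safe heel-supported walking is part of the hypothesis but has no endpoint or data item: the heel is last tested before surgery, and walking and falls are not systematically asked about.

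*Combined protocol and SAP*

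**What the plan says.** **Purpose.** Section 2.1 gives the reason for sparing the heel. With the existing ankle block, "the loss of cutaneous sensation and deep (or proprioceptive) sensation in the heel theoretically carries a risk of falling", so those patients go home on crutches and warned of that risk. Section 2.2 hypothesises that the selective block "would allow for both effective pain relief and safe resumption of walking with exclusive heel support", and describes pain relief and safe walking as a dual objective. Section 2.3.1 names as an aim of the study "promoting early resumption of unassisted walking (without crutches or splints) and rapid discharge from the hospital". The formal primary objective in section 3.1 is narrower: to "evaluate the feasibility and safety of a specific anesthesia technique for the distal foot, preserving sensation in the heel".

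**Measurement.** Under section 4.1, cold and touch tests run every 10 minutes up to 40 minutes after injection. The rule is: "The success of the selective block will be confirmed if the following results are obtained at 40 minutes", with a calcaneal score of 2 and both plantar scores at 0. Absence of paresthesia during the block is also part of the primary endpoint. Section 5.2.2 places the block 45 minutes before surgery.

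**Follow-up.** Section 4.2 assesses sensory-motor complications with Appendix 1 by telephone at Day 15±4, and at the 1-month surgical visit. The only postoperative entry in the data list of section 12.5 is "Possible complications (see Appendix 1: questionnaire". Appendix 1 has three yes/no items: reduced foot sensitivity, tingling or numbness, and difficulty moving the toes. Section 7 adds that adverse events are recorded in the eCRF at the same two contacts.

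**The concern.** The advantage claimed over the existing ankle block is that patients can walk safely on the heel without aids. The plan measures a precondition for that, a sensate heel before surgery, and then stops. It does not look at the heel when the patient first stands, at whether the patient walked, or at whether anyone fell.

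The study is a pilot meant to decide whether a comparative trial is worthwhile (sections 5.1 and 8.2). If it reports a high selective-block rate and few complications, readers will tend to take the walking claim as supported, although no data bear on it directly. The contacts at which the data could be collected already exist.

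**Working it through.** **1. The hypothesis set against the data collected.**

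| Item needed for the walking claim | Endpoints (4.1, 4.2) | Schedule (5.3) | Data list (12.5) | Appendix 1 |
|---|---|---|---|---|
| Heel sensation after surgery | no | no | no | first asked about Day 15, whole foot, not heel-specific |
| Walking with heel support | no | no | no | no |
| Walking aid used | no | no | no | no |
| Fall | no | no | no | no |

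The schedule does have a row for possible complications on Day 0, at Day 15±4 and at 1 month, and section 7 records adverse events at the last two. A fall could therefore be entered if the patient mentions it, but nothing prompts for it.

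**2. Timing of the last heel test.** Block 45 minutes before surgery (5.2.2); last test 40 minutes after injection (4.1). 45 − 40 = 5 minutes before surgery, if both times run from the same injection and the schedule is kept.

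**3. Can success be recorded although the heel is later numb?** Yes, by a route the protocol itself provides. If surgery cannot be performed, section 5.2.2 falls back on the standard tibial block at the ankle. Section 2.1 says that a tibial block at the ankle also anesthetises the calcaneal branches. A patient scored 2/0/0 at 40 minutes who then needs the fallback still meets the sensory criterion of the primary endpoint. Use of the fallback is logged (12.5) and counts against the surgical-feasibility endpoint (4.2), but heel status afterwards is not recorded. Later spread of the selective block to the heel would likewise go unseen.

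**4. The plan's own precision table.** Section 8.2 tabulates intervals for N = 50. The formula p ± 1.96 × √(p(1 − p)/50) reproduces it:
- p = 0.10: 1.96 × √(0.09/50) = 0.083, giving 0.017 to 0.183, width 0.166, as printed.
- p = 0.50: 1.96 × √(0.25/50) = 0.139, giving 0.361 to 0.639. The width is 0.277 against 0.278 printed, a rounding difference.
- The seven rows in between also agree.

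At p = 0 this formula gives an interval of zero width, so it cannot be used for a rare event such as a fall. An exact interval is needed.

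**5. What 50 patients could say about falls if they were asked.** Exact two-sided 95% limits:
- 0 of 50: upper limit 1 − 0.025^(1/50) = 0.0711, or 7.1%.
- 1 of 50: 0.05% to 10.6%.
- With fallback patients set apart, the denominator shrinks. 0 of 45 gives 7.9% and 0 of 40 gives 8.8% (5 or 10 fallback patients, for illustration).

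The documents give no fall rate. The chance of seeing at least one fall in 50 is 1 − (1 − r)^50. For assumed rates r of 1%, 2%, 5% and 10% this is 39%, 64%, 92% and 99%.

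**The case against.** **The formal aim is the technique, not walking.** Walking is not named in the primary objective (3.1) or in the four secondary objectives (3.2). Establishing the selective block first and studying walking in a later trial is a legitimate way to stage a pilot. This stands to a degree: a reader might infer that the safety aim as a whole cannot be answered, and the documents do not support that. Paresthesia, sensory-motor complications and adverse events address the neurological part. It does not remove the gap, because sections 2.2 and 2.3.1 themselves present walking as an objective of the study.

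**Falls are not wholly unrecorded.** A reader might infer that a fall could never enter the data. Section 7 shows otherwise, since adverse events go into the eCRF at both follow-up contacts. This stands, and limits the point to the lack of systematic questioning. An unprompted report gives a numerator that may be incomplete, and silence cannot be read as zero.

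**Loss of heel sensation after 40 minutes is speculative.** One might try to say by how many points heel sparing is overstated. Any such figure would only restate an assumed rate of late numbness. The documents give no data on late spread, and section 2.2 says the calcaneal branch generally arises above the injection line. This stands, and no such figure is claimed here.

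**Walking and fall data would be hard to attribute.** Patients given the fallback block do not represent the selective technique. Falls weeks later are not falls under the block. Several types of surgery are included, so use of crutches may reflect surgical instructions. These are fair points; they call for separate reporting, dates and descriptive use, not for leaving the items out.

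**Conclusion.** The concern holds in a limited form. The walking-safety part of the hypothesis has no dedicated endpoint or data item. The last heel test precedes surgery, and walking, walking aids and falls are not systematically asked about. The trial can report selective block and heel sensation at 40 minutes, together with neurological complications. It cannot report that the heel was still sensate when patients walked, or how many fell.

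The primary endpoint remains analysable, so this is a change that should be made and not a fatal flaw. As planned, there is no usable estimate of falls. With one question put to all 50 patients, 0 falls would bound the rate at 7.1%. That figure assumes that all 50 answer and that fallback patients are counted; separating them widens it as shown. The conclusion does not depend on any assumed rate of falls or of late heel numbness.

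**What to change.** - **Appendix 1:** add a question on whether the patient has fallen since surgery, and the date. State that it is asked at both the Day-15 call and the 1-month visit, since the form is titled for Day 15 only.
- **Day-0 eCRF and section 12.5:** add whether the patient walked with heel support, any walking aid used, and any fall.
- **Heel sensation:** where feasible, repeat the existing calcaneal score before discharge.
- **Sections 4.2 and 8.1:** list these as descriptive secondary safety outcomes with exact 95% confidence intervals. Use the dates to separate Day-0 falls from later ones, and report patients who received the fallback tibial block separately.

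These items record what happens and set no rule on mobilisation or treatment. The cost is a few minutes per patient at contacts that already exist, plus the corresponding eCRF and protocol changes.

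If the items are not added, limit the conclusion to selective block and heel sensation at 40 minutes plus neurological complications, and make no claim about safe walking.

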2.3.1. Expected benefits for the patient

The objective of this study is to provide long-lasting analgesia for forefoot surgery, while promoting early resumption of unassisted walking (without crutches or splints) and rapid discharge from the hospital.

2.3.2. Predictable and known risks

These include the risks associated with any anesthesia and surgery that are independent of the research. They are explained to patients during anesthesia and surgical consultations.

There are no risks specific to the study.

2.4. Description of the study population

Adult patients scheduled for forefoot surgery, such as metatarsal osteotomy, surgical treatment of ingrown toenails, foot wounds, foot infections, metatarsal fractures, or Morton's neuroma.

3. RESEARCH OBJECTIVES

3.1. Primary objective

The primary objective of the study is to evaluate the feasibility and safety of a specific anesthesia technique for the distal foot, preserving sensation in the heel.

3.2. Secondary objectives

1. To evaluate the feasibility of forefoot surgery.
2. To assess the ability to identify the plantar nerves at the ankle.
3. To assess patient satisfaction.
4. To evaluate the complication rate.

4. EVALUATION CRITERIA

4.1. Primary Endpoint

The primary endpoint is the success of the procedure, defined as the successful selective block of the plantar branches of the tibial nerve, anesthesia of the distal foot while preserving heel sensation, and the absence of paresthesia.

The success of the selective block of the plantar branches of the tibial nerve will be assessed using a sensation score for each branch of the tibial nerve.

A cold test and a touch test will be performed every 10 minutes for 40 minutes following the injection of local anesthetics.

The touch test will be performed using a 2-point sensitivity measurement device (Touch-Test).

The cold test will be performed using a cold roller (Rullo “Oerlikon” nizell.ch).

The tests will be performed on specific areas of the tibial nerve:

- calcaneal branches: calcaneus;
- medial plantar nerve: medial part of the arch of the foot;
- lateral plantar nerve: lateral part of the arch of the foot.

A contralateral assessment will be performed to accurately determine the sensory score.

Score/Contralateral side: 2: normal sensation, 1: decreased sensation, 0: total loss of sensation.

The success of the selective block will be confirmed if the following results are obtained at 40 minutes:

- calcaneal branches = 2
- medial plantar nerve = 0
- lateral plantar nerve = 0

At 40 minutes, a precise mapping of the plantar arch will be performed to determine the exact extent of sensory loss (Figure 4).

The degree of paresthesia during the procedure will be assessed by asking the patient about any sensations of discomfort: tingling, numbness, or other prickling sensations.

[figure not shown]

Figure 4: Example of a plantar arch mapping

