Based on the Practical Manual of Ultrasound-Guided Regional Anesthesia

Elsevier - Masson, Paris, 2014

Performing a superficial peroneal nerve block

E Albrecht, [name], H Cadas, V Moret.

adapted from Practical Manual of Ultrasound-Guided Regional Anesthesia
Published by Elsevier-Masson, Paris, 2014

- *Performing a saphenous nerve block*

An infiltration of the medial edge of the foot will be performed systematically.

- *Performing the specific lateral and medial plantar nerve block*

The line connecting the center of the medial malleolus and the medial calcaneal tuberosity (MC axis) will be marked prior to performing the block.

The ultrasound probe will be positioned at the medial edge of the foot below this line. The two plantar branches of the tibial nerve will be identified, as well as the tibial plantar arteries. The local anesthetic will be injected in contact with the neurovascular bundle.

The anesthesiologist will assess the identification of the plantar arteries and nerves below the MC axis using the ENR-Plantar Nerves protocol.

Position of the ultrasound probe for performing a block of the distal branches of the tibial nerve at the ankle

Sensory tests:

The cold test and touch test will be performed every 10 minutes for 40 minutes following the injection of local anesthetics into the specific territories of each nerve.

The anesthesiologist will record the sensory score for each branch of the tibial nerve.

At 40 minutes, a detailed sensory map of the sole of the foot will be created.

Recording of potential complications:

The occurrence of any paresthesia, indicative of nerve damage, will be noted. The anesthesiologist will ask the patient during the procedure about any sensations of discomfort: tingling, numbness, or other prickling sensations.

If regional anesthesia fails—defined as the inability to perform the surgery—the anesthesiologist will use the standard anesthesia technique: a tibial nerve block at the ankle above the mid-calf line.

b) Surgery

The surgical procedure will be performed according to standard practice.

Any intraoperative complications will also be noted.

The patient's satisfaction score will be assessed at the end of surgery.

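### The paresthesia component of the primary endpoint does not separate needle- or injection-evoked sensation from block onset, so a working block can be scored a failure

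*Combined protocol and SAP*

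**What the plan says.** Section 4.1 defines primary success as a composite. Besides a successful selective block it requires "anesthesia of the distal foot while preserving heel sensation, and the absence of paresthesia". Each territory is graded against the other foot: "Score/Contralateral side: 2: normal sensation, 1: decreased sensation, 0: total loss of sensation". At 40 minutes the calcaneal territory must score 2, with "medial plantar nerve = 0" and "lateral plantar nerve = 0". The same section assesses a degree of paresthesia "by asking the patient about any sensations of discomfort: tingling, numbness, or other prickling sensations".

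Section 5.2.2, under the recording of potential complications, gives the purpose: "The occurrence of any paresthesia, indicative of nerve damage, will be noted". It adds: "The anesthesiologist will ask the patient during the procedure about any sensations of discomfort". The same section has every patient receive blocks of the superficial and deep fibular, saphenous, and medial and lateral plantar nerves, which makes five.

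Section 8.1 treats the primary endpoint as a yes/no variable and estimates one proportion with a 95% confidence interval. Section 8.2 plans 50 patients. Section 5.6 states that the criterion is objective enough to rule out assessment bias. The data list in section 12.5 has the sensory scores at each 10-minute test and an entry for intraoperative complications. It has no paresthesia item, and no time or nerve for one.

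**The concern.** Numbness appears on both sides of the endpoint. A score of 0 in the plantar territories is complete numbness and is required for success. Numbness is also one of the sensations the patient is asked about to detect paresthesia, which means failure. The wording gives no time window, territory or type of sensation by which the anesthesiologist can tell an event evoked by the needle or the injection from the drug taking effect. With five nerves blocked in one session, a territory injected early may already be changing when the question is asked.

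The study is single-arm and open-label, so no comparator would absorb the error, and each anesthesiologist must decide alone whether reported numbness counts. The resulting proportion is meant to inform whether a comparative study follows (section 8.2). Paresthesia is also the Day 0 nerve-injury signal within a primary objective that includes safety (section 3.1).

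**Working it through.** **1. The plan's own figures.** The plan gives no number for paresthesia. Its only related figures are in the precision table of section 8.2, which is a Wald interval: P ± 1.96 × √(P(1 − P)/50).

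- P = 0.20: 1.96 × √(0.16/50) = 0.111, giving 0.089 to 0.311, as printed.
- P = 0.50: 1.96 × √(0.25/50) = 0.139, giving 0.361 to 0.639, as printed. The width is 0.277 against the printed 0.278, a rounding difference.

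All nine rows reproduce: limits to three decimals, widths to within 0.001. The table is sound. The problem is in what is counted, not in the sample size.

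**2. The texts side by side.**

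| Question | What the text gives |
|---|---|
| What is intended? | A sign of nerve damage (5.2.2) |
| What is asked? | Tingling, numbness, prickling (4.1, 5.2.2) |
| When? | During a *procedure* that could be needle placement, the 40-minute test period or surgery; in 5.2.2 the item follows the 40-minute tests |
| Which nerve? | Not stated; five are blocked |
| What counts? | A degree without scale or cut-off (4.1); any occurrence (5.2.2) |
| Can it be separated later? | Not from the list in 12.5, which has no paresthesia item, nerve or time |

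Read literally, a patient with the 2/0/0 pattern who truthfully reports a numb foot meets the failure criterion.

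**3. Direction and size.** Let S be the proportion of patients who are true successes, and q the share of those whose onset sensations are counted as paresthesia. Then

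observed success = S × (1 − q).

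This error turns successes into failures and never the reverse. Neither S nor q is in the documents; both are assumptions, shown as a range:

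| S | q = 0 | q = 0.10 | q = 0.25 | q = 0.50 |
|---|---|---|---|---|
| 0.70 | 0.700 | 0.630 | 0.525 | 0.350 |
| 0.80 | 0.800 | 0.720 | 0.600 | 0.400 |
| 0.90 | 0.900 | 0.810 | 0.675 | 0.450 |

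For S = 0.80 and N = 50 the Wald 95% intervals are 0.689 to 0.911 (q = 0), 0.596 to 0.844 (q = 0.10), 0.464 to 0.736 (q = 0.25) and 0.264 to 0.536 (q = 0.50). Each 10% misclassified costs 0.1 × S, that is 7, 8 or 9 percentage points for S = 0.70, 0.80 or 0.90.

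**4. Against the planned precision.** At S = 0.80 the half-width is (0.911 − 0.689)/2 = 0.111 and the shift is 0.80 × q. They are equal at q = 0.111/0.80 = 0.139. Beyond about 14% misclassified, the shift exceeds the sampling uncertainty that the interval shows. More patients would narrow the interval around the wrong value.

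**The case against.** The best defence is that context narrows the question. Section 5.2.2 files it under complications within the anesthesia part, apart from surgery, and ties it to nerve damage. Both sections speak of discomfort. Elsewhere in 5.2.2 *procedure* mostly means needle placement, whereas the score of 0 is read later, at 40 minutes. On that reading the two components differ in time and in kind. This is probably the intent, and it stands as such. It does not settle the matter, because the term is never defined, the item is listed after the 40-minute tests, and numbness is an explicit prompt.

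The damage is also partly contained. The 2/0/0 proportion can be calculated from the sensory scores alone, and nerve symptoms are asked about again at Day 15±4 and at 1 month. The study is an exploratory pilot with no success threshold. Section 5.2.2 records occurrence, which partly answers the point about degree. All of this stands, but none of it rescues the composite, which is the declared primary endpoint.

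A reader might infer that a faster or denser plantar block is the more likely to fail, or that the conflict persists even if the question is confined to the plantar injection. The documents support neither. They give no onset time. They describe the plantar block last, without mandating the order; if that order is followed, early numbness would come from the other nerves.

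**Conclusion.** The point holds as a defect of definition. As written, the primary endpoint allows a patient with a working block to be scored a failure, and the listed data would not allow this to be undone afterwards. The statement in section 5.6 that the criterion is sufficiently objective is not supported for this component.

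The direction is certain for this kind of error: success falls and the Day 0 paresthesia count rises. The size is not known. The figures of 72% and 60% from an assumed true 80% rest on assumed misclassification of 10% and 25%. They show sensitivity and are not a forecast. A reader might conclude that the success proportion is biased downward by a known or large amount. The documents support only that it could be, since an anesthesiologist who follows the evident intent may misclassify few patients or none.

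**What to change.** In sections 4.1 and 5.2.2:

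- Define endpoint paresthesia as any abnormal sensation, including tingling or prickling, evoked at needle contact or during injection of a given nerve.
- Have the question asked at each needle placement and answered yes or no.
- State that numbness or tingling that develops gradually after injection in a blocked territory is block onset and does not count.
- Remove numbness from the prompts.

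The definition should not be narrowed to shooting or electric sensations. That would discard tingling and prickling at needle contact, which the protocol counts, and could understate the safety signal.

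In section 12.5, add a dedicated eCRF item for paresthesia with nerve and time. In section 8.1, report the 2/0/0 block-success proportion and the paresthesia proportion separately, each with its 95% confidence interval, beside the composite.

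The cost is a few sentences, one eCRF field and a question repeated at each placement. No patients or procedures are added. The change has to precede data collection to be useful, because the listed data do not permit the separation later.

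### The paresthesia component of the primary endpoint does not exclude expected block sensations, so a patient with a working selective block can be scored as a failure

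*Combined protocol and SAP*

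**What the plan says.** Section 4.1 defines success of the procedure as a successful selective block of the plantar branches together with "anesthesia of the distal foot while preserving heel sensation, and the absence of paresthesia". Sensation is scored against the other foot as "2: normal sensation, 1: decreased sensation, 0: total loss of sensation". The selective block is confirmed at 40 minutes by a heel score of 2 with "medial plantar nerve = 0" and "lateral plantar nerve = 0".

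The same section then says how the degree of paresthesia is ascertained while the procedure is under way: by "asking the patient about any sensations of discomfort: tingling, numbness, or other prickling sensations".

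Section 5.2.2 repeats the question under the recording of potential complications and adds "The occurrence of any paresthesia, indicative of nerve damage, will be noted". It also states that all patients receive blocks of the superficial and deep fibular, saphenous, and lateral and medial plantar nerves, without premedication or deep sedation, although light sedation may be offered for significant discomfort.

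Section 8.1 treats the primary endpoint as a yes/no variable and estimates one proportion with a 95% confidence interval. Section 12.5, which lists the data to be collected, has sensory scores every 10 minutes and a plantar map. For events during the session it has only the general item "Intraoperative complications".

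**The concern.** One component of the composite requires complete loss of plantar sensation. Another requires that the patient not report paresthesia, and numbness is one of the sensations asked about. Followed literally, the text allows the intended drug effect to count against the patient. Tingling as a block sets in raises the same problem.

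The success proportion is the study's main result, and section 8.2 says its purpose is to judge quickly whether the method merits a comparative study. If some successes are failed for an expected sensation, the proportion is too low, and its confidence interval will not show this. Two anesthesiologists could also score the same patient differently while both follow the protocol. That sits badly with the statement in section 5.6 that the criterion is objective enough to avoid assessment bias.

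**Working it through.** **Step 1: the rules side by side.**

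- *Plantar component (4.1):* tested score of 0 in the medial and lateral territories, at 40 minutes after injection.
- *Heel component (4.1):* tested score of 2, at 40 minutes.
- *Paresthesia component (4.1, 5.2.2):* absence of reported tingling, numbness or prickling during the procedure. No clock time, injection site or threshold is given.

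Take a patient with heel 2, medial 0 and lateral 0 at 40 minutes. While a later nerve was being injected, this patient answered that part of the foot already felt numb. If paresthesia means needle-evoked sensation, the patient is a success. If it means any of the listed sensations reported during the session, the patient is a failure. The text permits both scorings.

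**Step 2: can the overlap in time occur?** Five nerves are blocked in one session. Section 5.2.2 describes the plantar block last but fixes no order. The documents give no onset time earlier than the first test at 10 minutes. Overlap is therefore possible under the protocol, but its frequency is unknown.

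**Step 3: is there a rule from degree to yes/no?** Section 4.1 speaks of a degree, 5.2.2 of any occurrence, and 8.1 of a binary endpoint. No degree is tied to failure.

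**Step 4: the plan's own precision figures.** The table in 8.2 is a Wald interval, p ± 1.960 × √(p(1−p)/50).

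- p = 0.50: half-width 1.960 × √(0.25/50) = 0.1386, limits 0.361 to 0.639, width 0.277. The plan gives 0.361 to 0.639 and 0.278, which is the difference of the rounded limits.
- p = 0.20: half-width 1.960 × √(0.16/50) = 0.1109, limits 0.089 to 0.311, width 0.222, as stated.

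All nine rows reproduce to within 0.001.

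**Step 5: illustration of size.** Let b be the true success rate when only evoked paresthesia disqualifies. Let m be the share of those successes failed for an expected sensation. Neither value is in the documents; both are assumptions. The observed rate is b(1 − m).

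| b | m = 0 | m = 0.10 | m = 0.30 | m = 0.50 |
|---|---|---|---|---|
| 0.70 | 0.70 | 0.63 | 0.49 | 0.35 |
| 0.80 | 0.80 | 0.72 | 0.56 | 0.40 |
| 0.90 | 0.90 | 0.81 | 0.63 | 0.45 |

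For b = 0.80 and N = 50, the Wald 95% intervals are 0.689 to 0.911, 0.596 to 0.844, 0.422 to 0.698 and 0.264 to 0.536, from left to right.

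The downward shift is b × m. Because p(1−p) is symmetric, the half-width at 0.80 equals that at 0.20, which is 0.111. The shift exceeds it once m > 0.111/0.80 = 0.139, or about 14%.

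**The case against.** The strongest defence is that needle-evoked paresthesia was meant. Section 5.2.2 describes paresthesia as a sign of nerve damage, files it under complications and asks about discomfort during the procedure. In the anesthesia part of 5.2.2, the word procedure mostly refers to the nerve blocks. This is probably the intent. It does not settle the matter, because nothing in the text makes that reading operative: numbness is named, onset sensations are not excluded, and several nerves are injected in turn in patients able to report what they feel.

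Four stronger readings are tempting, and the documents do not support them.

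- *The two components contradict each other, so success is impossible.* They do not. One is a tested score at 40 minutes; the other is a report during the procedure. The same patient can meet both.
- *Paresthesia fails the selective block.* It does not. Section 4.1 confirms the selective block from the three sensory scores alone. Paresthesia can fail only the composite.
- *A low result could not be separated from poor heel sparing.* It could. Scores for each tibial branch are recorded (5.2.2, 12.5), so block success and heel sparing can be calculated without the paresthesia component. What cannot reliably be separated from the listed data is evoked from expected sensation.
- *There is nowhere to record paresthesia.* There is a general complications item in 12.5, and the schedule in 5.3 includes complications on Day 0. What is missing is a dedicated field.

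It is also fair to say that counting paresthesia from any of the injections is defensible, since the primary objective includes safety and all patients receive all the blocks.

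**Conclusion.** The concern holds as a defect in the definition of one component. The composite, read as written, can score a patient with a working selective block as a failure, because expected onset sensations are not excluded and no degree is tied to failure.

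The possible bias is downward. Its size cannot be derived from the documents, and a reader should not take it as established that the proportion will be biased. It could be zero if all assessors apply the needle-evoked reading. Under the assumed values above it ranges from modest to larger than the planned precision. That numbness is a block effect follows from the protocol's own score of 0. That tingling accompanies onset, and that either sensation would be reported while later nerves are being injected, are assumptions.

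The consequence is limited by the exploratory, single-arm design with no success threshold, and by the fact that the sensory components are recoverable. It still affects the primary result, and the repair is simple.

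**What to change.** In sections 4.1 and 5.2.2:

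- Define disqualifying paresthesia as a sensation evoked by needle advancement or injection, with the question asked at that moment.
- Remove numbness from the sensations that disqualify, and exclude sensations that appear as the block sets in.
- Replace the unspecified degree with a stated yes/no rule.
- State whether evoked paresthesia at the fibular and saphenous injections counts toward the composite. Either choice is acceptable and is the sponsor's to make.

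In section 12.5, add a yes/no paresthesia field for each nerve instead of relying on the general complications item.

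In section 8.1, report the composite and, beside it, each component (both plantar scores 0, heel score 2, evoked paresthesia) with its own 95% confidence interval.

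The cost is a wording amendment and a few eCRF fields. No procedure is added and N = 50 is unchanged.
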